### **Statistical Analyses:**

Neither masking nor randomization will be employed for operation of this study; this is an open-label study

- Primary efficacy endpoints will be analyzed using descriptive statistics and restricted maximum likelihood repeated measures mixed model (REMLMMRM) models.
- Multiplicity adjustments of observed significance levels for primary efficacy endpoints will be presented.

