- Mean CFB in total conjunctival staining score at Week 12
- Mean CFB in central corneal staining score at Week 12
- Mean CFB in tear osmolarity at Week 12
- Mean CFB in frequency of ATP use at Week 12
- Mean CFB in unanaesthetized Schirmer's score at Week 12
- Percentage (%) of subjects who prefer study treatment over prior treatment at Week 12

Overall Study Design

This is an open-label, multisite, single-arm, phase IV clinical study that will evaluate the efficacy of Cequa™ cyclosporine 0.09% ophthalmic emulsion in patients with DED that is not well controlled by cyclosporine 0.05% ophthalmic emulsion. Subjects will be enrolled in up to 10 clinical sites throughout the United States. Informed consent will be obtained prior to any study specific procedure is performed.

Subjects who withdraw or are withdrawn/discontinued from the study after they have signed the informed consent and received the study treatment will not be replaced. This is an Electronic Data Capture (EDC) study utilizing web-based electronic case report forms. The study is designed using Celes web-based EDC system. KCT Data Management, Inc. will manage the EDC system according to their standard operating procedures throughout the study.

Analysis Populations:

Two analysis populations will be defined for this study: Safety (SAF) and Intent-to-Treat (ITT). The determination of which subjects will be included in each population will be made prior to locking the final database. All efficacy variables will be analyzed using the ITT set of subjects, and all safety variables will be analyzed using the SAF set of subjects.

Safety Analysis Population:

All patients who receive at least 1 dose of the study medication will be included in the SAF population. No subjects (or data) will be excluded because of protocol deviations that occur during the study.

Intent-to-Treat Population:

The Intent-to-Treat (ITT) population will be comprised of all subjects who receive at least 1 dose of the study medication and have at least 1 post-baseline assessment. Following the ITT principle, subjects will be analyzed irrespective of dosing compliance or any deviations in the study medication received.

Efficacy Analyses:

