The efficacy analysis will be performed after all subjects have completed Week 12 or discontinued prior to Week 12, and after the study database has been cleaned, verified, and locked. All efficacy analyses will be performed using the ITT population. All analyses will be implemented using SAS® version 9.4 or later (SAS Institute,Inc., Cary, NC).

Statistical Methodology:

Summary statistics will be presented for continuous variables with descriptive statistics, including n, mean, standard deviation (SD), median, minimum, and maximum. For categorical variables including binary variables, frequency counts and percentages will be presented. P-values will be computed for each analysis group separately. In addition, 95% 2-sided confidence intervals (CIs) will be presented, where relevant. In case of percentages, the CI will be computed using the Clopper-Pearson method. The CI will be computed for continuous variables using t-test analysis. Summary statistics will be displayed by baseline groups.

Demographics and Baseline Characteristics:

Demographics will be presented in a summary table and in a by-subject listing, including age, gender, race, iris color, and ethnicity. Baseline characteristics, presented in a summary table and in a by-subject listing.

Prior Medical, Ocular and Treatment History:

All medical and ophthalmic histories reported at the screening and baseline visits will have their verbatim term mapped to their corresponding thesaurus terms using version 25.1 of the Medical Dictionary for Regulatory Activities (MedDRA) coding dictionary.

Efficacy Analysis:

Primary Efficacy Analysis

The primary efficacy endpoint parameters for the study are the mean CFB in total CFS and the mean CFB in modified SAnDE score at Week 12. Significance will be set at p<0.05 for the analysis of all groups and endpoints.

Secondary Efficacy Analysis:

Same as primary

Safety Analyses:

All safety analyses will be performed using the SAF population. No imputation of missing data will be performed. Safety analyses will be presented in summary tables and in by-subject listings.

Compliance:

Drug accountability data was assessed at each visit and used for further patient counselling but was not collected for analysis.

Adverse Events:

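### Each secondary endpoint may be declared significant at p<0.05 on its own, with no order, no gate behind the primaries and no supportive label

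*SAP*

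**What the plan says.** Under Primary Efficacy Analysis, the SAP names two primary parameters at Week 12, change from baseline in total corneal fluorescein staining and in modified SAnDE score, and then states: "Significance will be set at p<0.05 for the analysis of all groups and endpoints". Under Secondary Efficacy Analysis the complete text is "Same as primary".

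The SAP's list of secondary endpoints has six entries. Five are mean changes from baseline at Week 12: total conjunctival staining, central corneal staining, tear osmolarity, frequency of ATP use and unanaesthetized Schirmer's score. The sixth is of another kind: "Percentage (%) of subjects who prefer study treatment over prior treatment at Week 12".

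Under Statistical Methodology, the SAP says that "95% 2-sided confidence intervals (CIs) will be presented, where relevant", t-based for continuous variables and Clopper-Pearson for percentages. It also asks for separate p-values in each analysis group, without saying how many groups there are.

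Multiplicity is mentioned once in the two documents, in the protocol synopsis under Statistical Analyses: "Multiplicity adjustments of observed significance levels for primary efficacy endpoints will be presented". That sentence names no method and does not extend to the secondary endpoints. The SAP does not repeat it.

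**The concern.** The SAP is not silent here; it gives a rule. Because the rule covers all endpoints, the secondaries cannot be read as descriptive by default. Each is judged alone at the full 5%, whatever happens on the primaries or on the other secondaries. Neither document gives a testing order, a gate, a division of alpha or a supportive label. Adjusting the two primaries, as the protocol synopsis intends, would leave the secondary family as it is.

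The SAP states that its goal is to evaluate the clinical benefits of switching products. Under the plan as written, a report could say that the switch significantly improved, for example, tear osmolarity when neither primary had shown a change. The study has no comparator arm against which to check such a statement.

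Preference raises a second, smaller problem. It is recorded once, at Week 12, so there is no change from baseline to analyse as the primaries are analysed. No reference percentage is stated either. The rule nevertheless calls for a p<0.05 judgement on it, and the analyst would have to choose a null value that the SAP does not supply.

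**Working it through.** There is no planned figure to reproduce: the documents give no sample size, power or family-wise error rate. The check asks what the stated per-test level implies for the family.

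**Inputs**

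- Per-test level: 0.05 (SAP, Primary Efficacy Analysis), carried to the secondaries by Secondary Efficacy Analysis.
- Sidedness: two-sided, critical value 1.96. This is taken from the two-sided confidence intervals; the SAP does not state the sidedness of the tests.
- Number of tests: 5, the change-from-baseline secondaries. Preference is left out because it has no stated null.
- Correlation between the test statistics: not given. A common value ρ is assumed and varied from 0 to 0.9.
- All five null hypotheses (no mean change) are taken as true.
- Testing by group: not counted, because the number of groups is not given.

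**Independent tests**

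- At least one p<0.05 in either direction: 1 − 0.95^5 = 1 − 0.7738 = 0.2262.
- At least one false finding of benefit, at 0.025 per test: 1 − 0.975^5 = 1 − 0.8811 = 0.1189.

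**Correlated tests**

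With equicorrelated standard normal statistics, oriented so that positive values favour benefit, and c = 1.96:

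P(at least one) = 1 − ∫ φ(t) · [Φ((c − √ρ·t)/√(1−ρ)) − Φ((−c − √ρ·t)/√(1−ρ))]^5 dt

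For the benefit direction alone, the second Φ term is dropped. Numerical integration gives:

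| Common ρ | Any p<0.05, five tests | False benefit, five tests |
|---|---|---|
| 0 | 22.6% | 11.9% |
| 0.3 | 20.9% | 10.5% |
| 0.5 | 18.3% | 9.2% |
| 0.7 | 14.8% | 7.4% |
| 0.9 | 10.2% | 5.1% |

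Against the per-test levels, the two-sided rate is 10.2/5 = 2.0 to 22.6/5 = 4.5 times as large. The false-benefit rate is 5.1/2.5 = 2.0 to 11.9/2.5 = 4.8 times as large.

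**With adjustment**

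Bonferroni over five tests (also the first step of Holm) uses 0.05/5 = 0.01 per test. The family rate is then 1 − 0.99^5 = 4.9% if the tests are independent, and at most 5% under any correlation.

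**The case against.** The best counter-argument is that nothing promised has been broken. The SAP sets a per-test threshold. It never claims 5% control over the secondaries, and it does not say that a significant secondary would support a claim. The secondary objective is only to evaluate changes in further signs and symptoms, and this is a phase 4 study of an approved product at its approved regimen. Unadjusted secondary p-values are common in that setting. This much stands: the gap is one of labelling, and formal error control is not obligatory. It does not remove the point, because the SAP attaches the word significance to every endpoint and applies no label at all.

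A reader might go further and infer that the family-wise error is 18% to 21% where 5% was promised. The documents do not support that, for three reasons. The figures need a common correlation of 0.5, which neither document gives. The upper one (20.7%) counts preference as a sixth test, although the SAP states no null for it and its specific provision for percentages is counts, percentages and a Clopper-Pearson interval. And 5% was never stated as a family rate. The two-sided figures also count false worsening; the rate that matches the harm described is the false-benefit rate, about half as large.

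It is also fair to say that the all-nulls-true case may be remote. Subjects enter on staining and symptom thresholds and there is no control arm, so regression to the mean or a trial effect could produce real mean changes whatever the drug does. Such changes could pass adjusted thresholds too. This limits what any multiplicity remedy can achieve.

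Finally, the public protocol is a synopsis, while the SAP refers to the full Version 1.0. The full text might say more about the secondaries. The criticism therefore rests on the SAP's own rule, which would still need to agree with it.

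**Conclusion.** The point holds as a modest, inexpensive improvement to the SAP. As written, any one secondary at nominal p<0.05 may be called significant even if both primaries fail.

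For the five change-from-baseline secondaries, the chance of at least one nominally significant result is about 10% to 23%, and the chance of at least one false finding of benefit is about 5% to 12%. Both ranges assume that all five nulls are true and that the tests are two-sided with a common correlation between 0.9 and 0. The direction of the conclusion does not depend on the correlation: the family rate is at least about twice the per-test level throughout. Testing in several groups could raise it, by an amount that cannot be calculated from the documents.

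For preference, the p<0.05 rule cannot be carried out as stated. The primary analyses are not affected by this point.

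**What to change.** Replace the text under Secondary Efficacy Analysis with: *Secondary endpoints are supportive. Estimates and 95% two-sided CIs (t-based for change from baseline, Clopper-Pearson for preference) will be presented. P-values are nominal, and no secondary endpoint will be declared statistically significant.* Limit the p<0.05 sentence under Primary Efficacy Analysis to the primary endpoints.

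This changes SAP wording only. It needs no new data, patients or procedures, and every planned estimate and interval is kept. The downside is that some secondaries that would have been called significant become descriptive.

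If the sponsor wants significance claims on secondaries, Holm at two-sided 0.05 over the five change-from-baseline endpoints, tested only after primary success, is an option, with preference reported outside the tested family. The SAP must first define primary success, since it does not say whether one or both primaries must be met. The cost is a stricter threshold, 0.01 at the first step.

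Neither route removes bias from the open-label, single-arm design. Any report of the secondaries should say so.
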